The pragmatic trial demonstration project is designed to test the implementation of efficient, high quality screening and intervention for PTSD and comorbidities across 24 US level I trauma center sites. The investigation will employ a stepped wedge cluster randomized design. In the stepped wedge design, level I trauma center sites are randomized sequentially to initiate the intervention. In the UH3 implementation phase, after IRB approval is obtained, each of the 24 trauma center sites will be randomized to one of four waves. All sites will begin with control patient recruitment and each wave is assigned a specific proportion of control and intervention patient recruitment. Wave one recruits 8 control and 32 intervention patients, wave two recruits 16 control and 24 intervention, wave three recruits 24 control and 16 intervention, and wave four recruits 32 control and 8 intervention patients. The demonstration project aims to recruit 960 patients, 40 at each trauma center site.

A routine trauma center provider, the site PTSD intervention champion, will be selected to orchestrate screening and intervention procedures. All sites will work with the study team to implement an EHR initial PTSD risk evaluation. Patients identified by EHR evaluation as at-risk for high early PTSD symptom levels (i.e., a score of \geq 3 risk domains positive) will then be formally screened for study entry with the patient reported outcome measure, the PTSD Checklist. Formal study cohort definition occurs with the PTSD Checklist; patients scoring \geq 35 on the PTSD Checklist will be followed in the longitudinal portion of the investigation.

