The **primary aim** of the UH3 period is to conduct a pragmatic randomized effectiveness trial of a collaborative care intervention targeting PTSD and comorbid conditions after acute care injury hospitalization. The investigation aims to determine if injured patients receiving the collaborative care intervention demonstrate significant reductions in PTSD symptoms when compared to control patients receiving care as usual. The study also aims to determine if the intervention patients when compared to control patients will demonstrate significant reductions in depressive symptoms and alcohol use problems, and improvements in physical function. An exploratory aim of the investigation is to assess the effectiveness of the intervention in injury survivors with and without pre-existing chronic medical conditions and with and without TBI. Exploratory analyses will also assess whether the intervention successfully reduced enduring symptom development for other co-morbid presentations (e.g., suicidal ideation, physical pain, drug use problems).

The **primary hypothesis** is that the intervention group when compared to the control group will demonstrate significant reductions in PTSD symptoms over the course of the year after injury. **Secondary hypotheses** are that intervention patients when compared to control patients will demonstrate, significant reductions in depressive symptoms, significant reductions in alcohol use problems, and improved post-injury physical function.

2. UH3 statistical analysis plan

All primary statistical analyses will be conducted using intent-to-treat methods. The primary goal of the statistical analyses is to examine and compare trends over time in the symptoms of PTSD. The major test of the intervention effect will be the change in PTSD symptoms from baseline to the 12-month study endpoint. We will also examine changes in PTSD symptoms from baseline to the 3- and 6-month study time points, as well as the treatment group by time by interaction for PTSD symptoms over the course of the 12 months after injury. This analytic approach will be replicated for all secondary outcomes; secondary analyses will examine trends over time for depression and alcohol use, and physical function. The major outcome variables are the continuous and dichotomous assessments of PTSD (PTSD Checklist), alcohol use problems (AUDIT), depression (PHQ-9), and physical function (MOS SF-36 PCS).

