The study team will use ANCOVA/mixed effects regression models to test the hypotheses. The investigative group has extensive experience with these analytic approaches in the analyses of longitudinal data after injury. These analytic approaches allow for the modeling of longitudinal data on patients, nested within trauma center sites (see also sample size and power discussion below for a more in-depth discussion of clustering). An important potential advantage of using longitudinal mixed models is the ability to use partial data on those of subjects with missing data, and therefore potentially ameliorate selection bias due to drop-out. In addition, mixed models naturally structure patient and center heterogeneity specifically allowing for random effects such as individual intercepts and slopes on time. Longitudinal regression models also allow the use of baseline covariates that may be prognostic or reflective of the study design.

Exploratory analyses will assess the impact of the intervention on primary and secondary outcomes for patients with and without pre-injury chronic medical conditions and with and without TBI. Exploratory analyses will also assess for significant reductions in suicidal ideation, pain and drug use problems in intervention patients when compared to control patients. The study team will again use ANCOVA/mixed effects regression for these exploratory analyses.²⁹⁴⁻²⁹⁷ In order to assess for potential selection bias across clusters, demographic characteristics (e.g., gender, ethnicity, insurance status) will also be tested as main effects and interactions with treatment status.

3. Stepped wedge cluster randomized design

Variability in multiple trauma center characteristics can impact rates of recruitment (e.g., admission volumes, EHR capacity), rates of PTSD (e.g., percentages of patients with violent injury admissions, intensive care unit admission rates), and the ability to follow patients longitudinally (e.g., patient demographic characteristics such as being homeless, clinical characteristics such as substance use problems). The study team initially considered using a stratified randomization procedure; however given the potential variability in multiple trauma center characteristics the study team will use a stepped wedge cluster randomized design for the UH3

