protocol. The stepped wedge design randomizes level I trauma center sites to sequentially initiate the intervention, thus allowing within site pre-, post- intervention comparisons, as well as between site comparisons. An additional advantage of the stepped wedge design for the UH3 protocol is that it would be impractical to roll out the entire intervention at 24 sites simultaneously. Finally, from an implementation science perspective there is an advantage to having the intervention ongoing at the end of the study at every site, should the intervention demonstrate a significant impact on PTSD and comorbidity. Given that there is little threat of contamination at each site across intervention and control patients and that the UH3 can accommodate the increased potential length of active recruitment and follow-up, the stepped wedge design appears to be an optimal choice for the UH3 protocol. In the proposed UH3 protocol stepped wedge design, all 24 participating level I trauma centers are randomly assigned to 1 of four waves. Each wave is assigned a specific proportion of control and intervention patient recruitment. Wave 1 recruits 8 control and 32 intervention patients, wave 2 recruits 16 control and 24 intervention, wave 3 recruits 24 control and 16 intervention and wave 4 recruits 32 control and 8 intervention patients. Interventions are initiated in the second six months of the UH3. The proposed stepped wedge design is outlined in the figure below.

Figure 16. Stepped Wedge Cluster Randomized Design

The stepped wedge regression model will adapt the functional form given below, and uses a timedependent variable to code treatment status for cluster *k* at calendar time *t*, denoted as condition_{kt.} For the stepped wedge study design there are now two key time scales: Period, which denotes the study period measured relative to the calendar time when the overall study begins; and Follow-up time which is a patientspecific time scale relative to when they enrolled in the study. In this model mean outcomes may have a temporal trend in calendar time and this will be captured by modeling "Period", while the primary outcome will still be the 12-month patient outcome denoted by Y_{ijkt} where i=4.

A) The primary analysis regression model will adapt the functional form given below:

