 $Y_{4jkt} = \beta_0 + \beta_1^* \text{Period}_{4jk1} + \beta_2^* \text{Period}_{4jk2} + \beta_3^* \text{Period}_{4jk3} + \beta_4^* \text{Period}_{4jk4} + \beta_5^* Y_{1jkt} + \beta_6^* \text{condition}_{kt} + \text{Mean model}$

Trauma center random effect and error

 $b_{k,0} + e_{4jkt}$

For this analysis the null hypothesis of no intervention effect is captured by H_0 : $\beta_6=0$, and the primary statistical test will be a Wald test of this null hypothesis.

B) A secondary analysis will explore the potential for treatment effect heterogeneity at the center level through inclusion of an additional random effect that permits cluster-specific variability in the intervention impact, captured by a random coefficient on the time-varying condition covariate:

 $Y_{4jkt} = \beta_0 + \beta_1 * \text{Period}_{4jk1} + \beta_2 * \text{Period}_{4jk2} + \beta_3 * \text{Period}_{4jk3} + \beta_4 * \text{Period}_{4jk4} + \beta_5 * Y_{1jkt} + \beta_6 * \text{condition}_{kt} + \text{Mean model}$

 $b_{k,0} + b_{k,1}$ *condition_{kt} + e_{4jkt}

Trauma center random intercept, slope, and error

The key difference for this model is that the intervention effect at trauma center k would be allowed to vary across centers and would involve the overall average intervention effect and a center-specific random intervention effect: β_6 + $b_{k,1}$. For this analysis the null hypothesis of a null average intervention effect is still captured by H₀: β_6 =0, and the primary test will be a Wald test of this null hypothesis, but now using an additional random intervention effect together with a standard random trauma center effect (random intercept).

C) A secondary analysis will evaluate the impact of intervention at all of the longitudinal follow-up times by including additional outcome measures and associated follow-up time variables, and interactions between follow-up time and intervention:

$$\begin{split} Y_{ijkt} &= \beta_0 + \beta_1 * \text{Period}_{ijk1} + \beta_2 * \text{Period}_{ijk2} + \beta_3 * \text{Period}_{ijk3} + \beta_4 * \text{Period}_{ijk4} + \beta_5 * \text{Followup}_{2jkt} + \beta_6 * \text{Followup}_{3jkt} + \\ \beta_7 * \text{Followup}_{4jkt} + \beta_8 * \text{condition}_{kt} + \beta_9 * \text{Followup}_{2jkt} * \text{condition}_{kt} + \beta_{10} * \text{Followup}_{3jkt} * \text{condition}_{kt} + \\ \beta_{11} * \text{Followup}_{4jkt} * \text{condition}_{kt} + \\ \end{split}$$

Mean model

a _{jk,0} + a _{jk,1} *Followup _{ijkt} +	Patient random effects

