$b_{k,0} + b_{k,1}$ *condition _{kt} + e_{ijkt}	Trauma center random effects and error

Y_{ijkt} denotes patient outcome at follow up time i (i=1,2,3,4) (baseline, 3m, 6m, 12m)

for patient j ($j=1,2,...,n_k$)

at trauma center k (k=1,2,...,24)

enrolled in time period t (t=0,1,2,3,4)

For secondary analysis using the repeated measurements from each subject there are two key hypotheses to test. First, the 12-month intervention effect would now be captured by the intervention-by-time interaction specific to the 12-month assessment time: H_0 : β_{11} =0; and evaluation of the intervention effect under this model evaluates any impact of using the partially complete longitudinal data for all subjects to estimate the 12-month intervention effect. This analysis provides a sensitivity analysis evaluating the impact of missing 12-month data for subjects who do have partial follow-up data (e.g. 3 month, 6 month data). A second exploratory hypothesis would be the global null of no intervention effect at all follow-up times, and this would be captured by the multivariate null hypothesis: H_0 : $\beta_8 = \beta_9 = \beta_{10} = \beta_{11} = 0$; and evaluated using a multivariate Wald test. Under this hypothesis the intervention and control means within a given period would be equivalent for all patient follow-up times.

The primary analysis is a single hypothesis test based on Model (A) and will use alpha=0.05. All other statistical tests are conducted to evaluate the sensitivity of the primary analysis to either heterogeneity or missing data, and therefore multiple comparison corrections are not used for these secondary analyses.

Subject Attrition: Some attrition is expected in the study sample due to the research context and the population under study (i.e., low income, ethnoculturally diverse, injured trauma survivors). Prior studies by the

investigative group have consistently achieved follow-up completion rates \geq 75-80% at 12 months post-injury with this population. Estimates derived from these rates are incorporated into the descriptions of subject flow and power analyses.

4. Sample size and power

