A number of issues specific to the design and analyses of cluster randomized trials are addressed by the current power analyses.²⁹⁸⁻³⁰² A key consideration for the trial is the nesting of patients within trauma center sites and the ascertainment of associated intraclass correlations (ICC). The study team has extensive experience with prior multisite trauma center observational and pragmatic clinical trial investigations. Sample size estimates were therefore adjusted for the clustering of patients within trauma center sites, using appropriate ICCs derived from the study team's prior multisite investigations; original ICCs utilized included, PTSD Checklist ICC = 0.0083, PHQ-9 ICC = 0.0259, AUDIT ICC = 0.0059, SF-36 PCS ICC = 0.003.Original sample size estimates suggested recruiting 20 trauma center sites with a total study N = 800 patients (n = 40 patients per site).

Table 10. PTSD Checklist Effect Sizes					
	Intraclass Correlation				
PTSD Checklist	0.005	0.010	0.020	0.030	
Minimum Detectable Effect Size	0.216	0.220	0.227	0.231	

In response to a series of discussions with the NIH Health Care Systems Biostatistics Core, sample size estimates were revised using more conservative ICCs. The power analyses model the baseline to 12-month treatment effect for the primary outcome and secondary outcomes. Table 10, provides effect sizes for the PTSD Checklist with a range of ICCs that includes empirically derived ICCs from the investigative team's prior studies as well more conservative ICC estimates suggested by the NIH Health Care Systems Collaboratory Biostatistics Core. Table 11 delineates the parameters used to estimate power for the PTSD Checklist, PHQ-9, AUDIT, and SF-PCS. Sample size estimates were derived using the STATA statistical package.³⁰³ With each of the 24 trauma center sites recruiting 40 patients into the study, the study has 80% power to detect effect sizes ranging from 0.22 to 0.23. These effect sizes are smaller than our previously observed treatment effect for PTSD symptoms of 0.34. In prior investigations PTSD treatment effects of 0.34 have been associated with clinically significant and policy relevant functional outcome improvements.

Table 11. Stepped Wedge Power for UH3 Outcomes					
Continuous outcomes	PTSD Checklist	PHQ9	AUDIT	SF-36 PCS	
Cluster size at baseline	40	40	40	40	
Cluster size estimation at 12m (25%	30	30	30	30	
attrition)					
Total Number of clusters	24	24	24	24	
alpha	0.05	0.05	0.05	0.05	
Power	0.8	0.8	0.8	0.8	

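### The single primary test uses only patients with a 12-month PTSD score; 3- and 6-month scores of patients lost by 12 months enter only a secondary model that cannot isolate the effect of missing data

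*Combined protocol and SAP*

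**What the plan says.** In the Statistical Analysis Plan, section 3 (Stepped wedge cluster randomized design), "the primary outcome will still be the 12-month patient outcome denoted by Y_{ijkt} where i=4". Model A regresses that score on period terms, the baseline score and condition, with a random intercept for trauma center. For the condition coefficient, "the primary statistical test will be a Wald test of this null hypothesis", and "The primary analysis is a single hypothesis test based on Model (A) and will use alpha=0.05". No imputation, weighting or missing-data assumption is given for Model A.

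Section 2 says "All primary statistical analyses will be conducted using intent-to-treat methods". It also names as an advantage of longitudinal mixed models "the ability to use partial data on those of subjects with missing data, and therefore potentially ameliorate selection bias due to drop-out". The Design Overview says the intent-to-treat outcome analyses will draw on the 3-, 6- and 12-month interviews as well as baseline data.

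The 3- and 6-month scores appear in Model C, which section 3 describes as a sensitivity analysis for missing 12-month data in patients with partial follow-up. Table 11 takes 25% attrition, from 40 to 30 patients per site. The attrition paragraph reports 12-month completion of at least 75-80% in earlier studies by the same group.

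**The concern.** The plan presents the use of partial data as protection against drop-out bias, then rests its one confirmatory test on a model with no such protection.

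There is reason to think loss will not be random. Section 3 of the SAP says the ability to follow patients varies with features such as homelessness and substance use problems. The two conditions also differ in contact: intervention patients have a care manager for up to six months, while controls receive nurse notification and usual care. If patients with high scores are lost more readily in one condition than in the other, a model restricted to 12-month completers gives a biased condition effect. The 3- and 6-month scores might have explained that loss. At stake is the validity of the primary estimate and its error rate, more than its precision.

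**Working it through.** **Inputs from the documents.** 24 sites x 40 = 960 enrolled; 24 x 30 = 720 with a 12-month score; four waves of six sites, five periods of 8 patients per site (6 after attrition); ICC 0.02; autocorrelation 0.7; SD 15; alpha 0.05 (taken as two-sided); power 80%.

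**Patients not contributing.** 960 x 0.25 = 240; 960 x 0.20 = 192.

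**Reproducing the plan's detectable effect.** The Hussey-Hughes variance is I s²(s² + Tτ²) / [(IU - W)s² + (U² + ITU - TW - IV)τ²], with I = 24, T = 5, U = 60, W = 1080, V = 180. Baseline adjustment multiplies the variance by 1 - 0.7² = 0.51.

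- s² = 0.51 x 0.98 / 6 = 0.0833; τ² = 0.51 x 0.02 = 0.0102.
- Numerator: 24 x 0.0833 x (0.0833 + 0.0510) = 0.2685.
- Denominator: 360 x 0.0833 + 1080 x 0.0102 = 41.00.
- Variance 0.00655, SE 0.081; detectable effect 2.80 x SE = 0.2267.

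For ICC 0.005, 0.010, 0.020 and 0.030 this gives 0.2161, 0.2203, 0.2267 and 0.2311. Table 10 states 0.216, 0.220, 0.227 and 0.231. With all 960 analysed the value at ICC 0.02 would be 0.200. The trial was therefore sized on 12-month completers, and power is not overstated on this account.

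**Bias of the completers-only analysis.** The assumptions are mine, not the documents': no true effect, 25% missing in each condition, correlation 0.7 between visits (6-to-12-month 0.7 or 0.8), and dropout log-odds linear in the 6-month score. With bias b, type I error = Φ(-1.96 + b/0.081) + Φ(-1.96 - b/0.081). For b = 0.025 this is 0.049 + 0.012 = 0.061.

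| 6-to-12-month r | Log-odds per SD, control / intervention | Bias (SD) | Type I error |
|---|---|---|---|
| 0.7 | 0.5 / 0.5 | 0 | 5% |
| 0.7 | 0.5 / 0.3 | 0.01 | 5.2% |
| 0.7 | 0.5 / 0 | 0.025 | 6.1% |
| 0.7 | 0.7 / -0.3 | 0.05 | about 9% |
| 0.8 | 0.7 / -0.3 | 0.07 | about 15% |

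On the PTSD Checklist, 0.05 SD is 0.05 x 15 = 0.75 points, against a detectable effect of 0.227 x 15 = 3.4 points. A separate simulation with the trial's site and period structure (r = 0.7, 800 runs per scenario) agreed. There was no bias with equal dependence, a shift of about 0.5 points at 0.7 / 0, and 1.0-1.1 points (about 0.07 SD) at the stronger opposite-sign setting 0.7 / -0.7. In these scenarios the bias hides benefit; the mirror-image pattern would create it.

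**What the earlier scores recover.** If every dropout has 3- and 6-month scores, using them leaves 0.002 SD or less. If only 40% have them, biases of 0.025-0.073 SD fall to 0.013-0.040 SD, so about half remains.

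**Precision** (ignoring clustering). Residual variance of the 12-month score is 0.51 given baseline, and 1 - 3(0.49)/2.4 = 0.3875 given three earlier visits at r = 0.7. The ratio 0.3875/0.51 is 0.760.

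- All 240 dropouts with earlier scores: 0.760 + 0.240 x 720/960 = 0.940. Variance falls 6%, effective N is about 766, and the detectable effect moves from 0.227 to about 0.22.
- 40% (96 patients): 0.760 + 0.240 x 720/816 = 0.972, a 3% fall.

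**Model A beside Model C.** Model C differs from Model A in more than the data used. It treats baseline as an outcome, tests the 12-month condition-by-time term β11 (a difference in change from baseline, with a baseline condition difference left free), and adds a random center-by-condition effect. A gap between A and C could come from any of these.

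**The case against.** The strongest defence is that the plan already deals with this: Model C is prespecified for exactly this purpose, so the proposal mostly exchanges two planned analyses. A reader might infer from the primary model alone that partial data are ignored; they are not. What remains is that Model A alone decides the trial, Model C is not a like-for-like check, and no rule covers disagreement between them.

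A reader might also infer a breach of intent-to-treat. The documents do not support that. Model A analyses patients by assigned condition, and the description of intent-to-treat in the conceptual framework section concerns adherence, not missing outcomes. The advantage quoted in section 2 is claimed for longitudinal mixed models, which Model C is and Model A is not. The remaining tension is with the Design Overview, which says the intent-to-treat analyses will use all the interviews.

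The bias figures rest on differential dropout for which the documents give no number. Follow-up interviews are blinded, the tracing procedures make no distinction by condition, and intervention ends at about six months, all of which may reduce any difference. Nor do the documents say how many patients lost at 12 months will have earlier scores.

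Finally, a repeated-measures model that forced one calendar trend on all visits would add an assumption that Model A avoids, which matters where condition is partly confounded with period. That is a fair objection to a careless version of the fix. It is met by letting period and baseline effects differ by visit.

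**Conclusion.** The point stands as a worthwhile, inexpensive improvement. It does not invalidate the design. The primary test leaves out an expected 192-240 of 960 patients and any interim scores they have. Model A is unbiased if missingness depends only on baseline score, condition, period and center, or depends on symptoms equally in both conditions. If symptom-related dropout differs by condition over the range tabulated, the bias is 0.01-0.05 SD at r = 0.7. About 0.07 SD requires opposite-sign dropout, either with a 6-to-12-month correlation of 0.8 or with a stronger imbalance at 0.7. It would be wrong to report 15% as the expected type I error or to call the trial underpowered. The case rests on protection against bias and a cleaner missing-data comparison; the variance gain is at most about 6% at r = 0.7.

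**What to change.** Make the primary model a likelihood-based repeated-measures version of Model A:

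- Outcomes: the 3-, 6- and 12-month PTSD Checklist scores, with baseline as a covariate and not as an outcome.
- Period, baseline and condition effects each interacting with follow-up visit.
- A site random intercept, allowed to differ by visit if estimable, and an unstructured within-patient covariance.
- One test at alpha 0.05: the 12-month condition contrast.

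Keep the present Model A as the completers sensitivity analysis, so that the two differ mainly in their use of the interim scores, and state the missing-at-random assumption.

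The cost is SAP wording and a larger model with a within-patient covariance to estimate; the interviews are already scheduled in Table 9. The new model protects only as far as dropouts have earlier scores and missing-at-random holds. The change should be made before outcomes are examined by condition.

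### Does the lack of a stated multiplicity policy for the PHQ-9, AUDIT and SF-36 PCS hypotheses leave their results open to interpretation after the fact?

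*Combined protocol and SAP*

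**What the plan says.** Section 1 of the Statistical Analysis Plan (Study aims and hypotheses) states one primary hypothesis, on PTSD symptoms. Under a separate label of secondary hypotheses, it expects that intervention patients "will demonstrate, significant reductions in depressive symptoms, significant reductions in alcohol use problems, and improved post-injury physical function". The outcome assessments section ranks the measures in the same way: the PTSD Checklist is primary, and the PHQ-9, AUDIT and SF-12/36 are secondary.

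Section 2 makes the baseline to 12-month change the major test and applies the same approach to the secondary outcomes. Further outcomes are marked down explicitly: "Exploratory analyses will also assess for significant reductions in suicidal ideation, pain and drug use problems".

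Section 3 sets out Models A to C and closes with the alpha statement: "The primary analysis is a single hypothesis test based on Model (A) and will use alpha=0.05". The next sentence gives the reason for leaving everything else uncorrected, "All other statistical tests are conducted to evaluate the sensitivity of the primary analysis to either heterogeneity or missing data", and concludes that "multiple comparison corrections are not used for these secondary analyses".

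Section 4, Table 11, lists alpha 0.05 and power 0.8 separately for the PTSD Checklist, PHQ-9, AUDIT and SF-36 PCS, with no split and no order.

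**The concern.** The waiver of correction rests on a reason, and the reason is untrue of three tests that it appears to cover. A test on the PHQ-9 is not a check on the robustness of the PTSD result. If the sentence is read literally, the secondary outcomes go uncorrected for a reason that does not apply to them. If it is confined to Models B and C, no sentence deals with the secondary outcomes at all.

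The case at stake is a mixed result: PTSD not significant, but depression, alcohol use or physical function significant. The trial is meant to inform national trauma-centre policy on PTSD and comorbidity, so a reader may ask whether such a result could be promoted to a positive finding, with the rule chosen once the data are known.

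**Working it through.** **Which tests the stated reason fits**

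- Model B: "A secondary analysis will explore the potential for treatment effect heterogeneity at the center level". The heterogeneity reason fits.
- Model C, 12-month interaction: "This analysis provides a sensitivity analysis evaluating the impact of missing 12-month data". The missing-data reason fits.
- Model C, joint test: "A second exploratory hypothesis would be the global null of no intervention effect at all follow-up times". The reason does not fit well, but the test carries its own exploratory label.
- PHQ-9, AUDIT and SF-36 PCS at 12 months: the reason does not fit. They are labelled secondary, and Table 11 gives each 0.05.

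**Reproducing the plan's power figures**

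Inputs from the plan: 24 sites, four waves, five periods, 30 completers per site at 12 months (25% attrition), autocorrelation 0.7, 80% power, alpha 0.05. Assumptions: equal waves of 6 sites, 30/5 = 6 completers per site-period, two-sided tests.

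The Hussey-Hughes variance is

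Var = Iσ²(σ² + Tτ²) / [(IU − W)σ² + (U² + ITU − TW − IV)τ²],

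with I = 24, T = 5, σ² = (1 − ICC)/6 and τ² = ICC. The design terms are:

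- U = 6(4+3+2+1) = 60
- W = 0² + 6² + 12² + 18² + 24² = 1080
- V = 6(16+9+4+1) = 180

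The bracket is therefore 360σ² + 1080τ². At ICC 0.02:

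- σ² = 0.1633
- Var = 24 × 0.1633 × 0.2633 / (58.8 + 21.6) = 0.01284, so SE = 0.1133
- With baseline adjustment, SE = 0.1133 × √(1 − 0.7²) = 0.0809
- Detectable effect = (1.960 + 0.842) × 0.0809 = 0.227

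At ICC 0.005, 0.010, 0.020 and 0.030 the results are 0.216, 0.220, 0.227 and 0.231, which are all four entries of Table 10. For the PHQ-9 at ICC 0.0259 the result is 0.230, as in the STATA row of Table 11. The plan's power therefore already assumes an unadjusted two-sided 0.05 per outcome.

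**False positives when all nulls are true**

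The documents give no correlation between outcomes. A common correlation of 0 to 0.7 among the test statistics is assumed, and correlated values come from simulation (2 million draws).

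| Event | Independent | Correlation 0.7 |
|---|---|---|
| At least one of three significant, either direction | 1 − 0.95³ = 14.3% | 10.9% |
| At least one of three significant, toward benefit | 1 − 0.975³ = 7.3% | 5.5% |
| PTSD not significant, at least one secondary toward benefit | 0.95 × 0.073 = about 7% | 4.0% |

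**The same mixed result when effects are real**

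| Assumed effects | Independent | Correlation 0.7 |
|---|---|---|
| All four at half the detectable size (0.113, power 0.289) | 0.711 × (1 − 0.711³) = 45% | 21% |
| All four at the detectable size (power 0.80) | 0.20 × (1 − 0.20³) = 20% | 14% |
| PTSD at 0.34, secondaries at the detectable size | 0.0125 × 0.992 = 1.2% | 0.3% |

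In the last row, 0.34/0.0809 = 4.20, which gives PTSD power of 0.9875. In all three rows every secondary effect is real by assumption, so a significant secondary test is a correct detection.

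**What a correction would cost**

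At 0.05/3 = 0.0167 per test, power at the detectable size falls from 80% to 65.8%, and the effect detectable with 80% power rises from 0.23 to 0.266. Under Holm, with all three secondary effects at the detectable size, average power is 0.75 (independent) to 0.73 (correlation 0.7), a loss of 5 to 7 points. The primary error rate does not change under either.

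**The case for a change.** The best argument for acting is that the secondary label does not settle everything. Section 1 of the Statistical Analysis Plan puts the three outcomes inside the primary-aim paragraph and makes statistical significance the criterion for two of them. The authors use the word exploratory elsewhere when they want to lower a test's standing, and they do not use it here. Section 2 also mentions 3- and 6-month changes and dichotomous versions, so the family can be counted larger than three. Nine tests (three outcomes at three times) would give 1 − 0.95⁹ = 37% if independent, although repeated measures on the same patients are not. Clarifying sentences would cost nothing and would have to be written before the results to be worth anything.

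Part of this stands. The reason given does not describe the secondary outcomes, and no sentence calls them supportive. Taking the continuous 12-month test as the relevant one for each is an inference, though a well-supported one: section 2 makes the 12-month change the major test, and Table 11 powers continuous outcomes.

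It does not follow that the interpretation is open. A plan with one named primary hypothesis, one test at 0.05 and three hypotheses labelled secondary already says which result decides the trial. Nothing in it allows a secondary finding to stand in for a failed PTSD test. Whether the secondary tests are adjusted also has an answer under either reading of the alpha statement. Literally, all other tests are uncorrected. On the narrow reading, no adjustment or order is prescribed and Table 11 shows 0.05 for each.

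**Conclusion.** No change follows. The sentence on correction gives an imprecise reason, and an analyst can fill the gap sensibly from the plan itself: test PTSD under Model A at 0.05, test the three secondary outcomes unadjusted at 0.05, and report them as secondary whatever the PTSD result. Unadjusted secondary tests beside one protected primary are a fair trade-off. Correction would cost power on those outcomes and buy nothing for the primary conclusion.

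The exposure is modest. The primary type I error stays at 0.05. Across the three secondary tests the chance of at least one false positive is 14.3% to 10.9%, and the chance of the mixed result arising wholly by chance is about 7% to 4%. The 45% to 21% and 20% to 14% figures describe limited power for real effects. With the plan's own earlier PTSD effect of 0.34, and secondary effects at the detectable size, the mixed result has probability 1.2% to 0.3%.

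These figures rest on two-sided tests, equal waves, and assumed correlations between 0 and 0.7. Stating the policy in words would record what the labels and Table 11 already imply and would alter no result.
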